When 419 PFS events have occurred the primary PFS analysis will be performed. The median time to PFS and corresponding two-sided 95% confidence intervals will be calculated using the product limit estimator and displayed using a Kaplan-Meier graph, by treatment group. A log-rank test stratified by hormone receptor status, number of prior HER2-directed regimens in the metastatic setting, visceral disease, and geographic region will be used to test the null hypothesis of no difference in the time to PFS between the two treatment groups at the alpha level of 0.01. When 378 deaths have occurred, the primary OS analysis (final analysis) will be performed, using similar methods. A log-rank test controlling for hormone receptor status, number of prior HER2-directed regimens in the metastatic setting, visceral disease, and geographic region strata will be used to test the null hypothesis of no difference in the hazard between the two treatment groups at the alpha level of 0.038.

The treatment difference in the secondary efficacy endpoints of ORR and CBR will be analyzed using a Cochran-Mantel-Haenszel (CMH) Chi-square test, stratified by the hormone receptor status, number of prior HER2-directed regimens in the metastatic setting, geographic region, and disease category (visceral vs. non-visceral only). The treatment difference in the secondary efficacy endpoints of DOR, and Investigator-assessed PFS will be analyzed using a product limit estimate of the median time to event. Differences between treatment groups will be examined using a log rank test statistic stratified by hormone receptor status, prior HER2-directed regimens in the metastatic setting, geographic region, and disease category (visceral vs. non visceral only) similar to the analysis for the primary endpoint. All time-to-event endpoints, including time to intervention for symptomatic CNS disease, will be displayed using Kaplan-Meier survival plots. Health outcomes assessments (EORTC QLQ-C30, EORTC QLQ-BR23 and EQ-5D-5L) will be analyzed using a random effects mixed model with treatment, time, number of prior HER2-directed regimens in the metastatic setting (binary), geographic region, site of metastases, and the treatment by time interaction.

Subjects who discontinue therapy early will be censored at their last available time point. Sensitivity analyses will be performed to investigate the impact of differential dropout between the 2 treatment groups on the treatment effect estimate.

Safety

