When 419 PFS events have occurred the primary PFS analysis will be performed. The median time to PFS and corresponding two-sided 95% confidence intervals will be calculated using the product limit estimator and displayed using a Kaplan-Meier graph, by treatment group. A log-rank test controlling for hormone receptor status, number of prior HER2-directed regimens in the metastatic setting, visceral disease, and geographic region strata will be used to test the null hypothesis of no difference in the time to PFS between the two treatment groups at the alpha level of 0.01. Subjects who discontinue therapy early will be censored at their last available time point. Sensitivity analyses will be performed to investigate the impact of differential dropout between the two treatment groups on the treatment effect estimate.

When the PFS analysis is performed, an interim analysis will be performed on the OS endpoint. When 378 deaths have occurred, primary OS analysis (final analysis) will be performed. The median time to PFS and corresponding two-sided 95% confidence intervals will be calculated using the product limit estimator and displayed using a Kaplan-Meier graph, by treatment group. A log-rank test controlling for hormone receptor status, number of prior HER2-directed regimens in the metastatic setting, visceral disease status, and geographic region strata will be used to test the null hypothesis of no difference in the hazard between the two treatment groups at the alpha level of 0.002 at the interim analysis and 0.038 for the final analysis.

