12.6 Interim Analyses

No interim PFS analysis for early stopping is planned. An interim OS analysis will be performed at the time of final PFS analysis.

The Lan-DeMets alpha spending function approach will be used to adjust the O'Brien-Fleming boundary if the timing based on the final PFS analysis does not correspond to the expected information time of half of the OS events (DeMets and Gordon Lan 1994; Cook 2003).

The hazard rate in the control arm for survival will be assessed to determine if the sample size or duration of follow-up or both should be adjusted to ensure timely achievement of the required 378 death events.

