12.7 Determination of Sample Size

The co-primary endpoints will be analyzed using an overall Type I error rate of 0.01 for PFS and 0.04 for OS. To detect a hazard ratio (control versus treatment) of 0.70 with approximately 85% power, 419 PFS events (PD/deaths) are required to be observed; this assumes a median (ITT) PFS of 8.0 months (34.7 weeks) for the experimental arm (neratinib plus capecitabine) and 5.6 months (24.3 weeks) for the control arm (lapatinib plus capecitabine). It is expected that the 419th event will be observed at approximately 26 months after the first patient is enrolled, which would correspond to approximately half of the death events needed to be observed. At this time, an interim analysis on OS will also be performed. For the OS endpoint, a group sequential method will be employed to maintain the overall Type I error rate at 0.04. Specifically, O'Brien-Fleming boundaries will be calculated to create appropriate critical values to which the log rank statistic will be compared.

Information Fraction	Expected Death Events	Study Month	Boundary (Reject H ₀)	Significance Level
50%	185	26	3.066	0.002
100%	378	50	2.058	0.038

These boundaries are designed to detect a hazard ratio (control versus treatment) of 0.725 with approximately 85% power. Overall, 378 events (deaths) are required to be observed; this assumes a median (ITT) OS of 30.3 months for the experimental arm (neratinib plus capecitabine) and 22.0 months for the control arm (lapatinib plus capecitabine). Approximately 600 patients will be enrolled and randomized equally between the two treatment arms.

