2.6. Sample Size Determination

The co-primary endpoints will be analyzed using an overall Type I error rate of 0.01 for PFS and 0.04 for OS. To detect a hazard ratio (experimental vs. control) of 0.70 with approximately 85% power, 419 PFS events (PD/Deaths) are required to be observed; this assumes a median (ITT) PFS of 8.0 months (34.7 weeks) for the experimental arm (neratinib plus capecitabine) and 5.6 months (24.3 weeks) for the control arm (lapatinib plus capecitabine).

It is expected that the 419th event will be observed at approximately 26 months after the first subject is enrolled, which would correspond to approximately half of the death events needed to be observed. At this time, an interim analysis on OS will also be performed. For the OS endpoint, a group sequential method will be employed to maintain the overall Type I error rate at 0.04. Specifically, Lan DeMets alpha spending function approximating the O’Brian-Fleming boundaries will be calculated to create appropriate critical values to which the log rank statistic will be compared (De Mets and Gordon Lan, 1994). If 50% of the deaths are observed at the interim OS analysis, the boundary using the Lan-DeMets alpha spending function is shown in Table 1 for OS interim analysis.

Table 1: Spending Function

Information Fraction	Expected Death Events	Study Month	Boundary (Reject H_0)	2-Sided Significance Level*
50%	185	26	3.066	0.002
100%	378	50	2.058	0.039

* This significance level relates to the 0.04 alpha allocation to OS but will be updated if the entire 0.05 can be allocated to OS.

These boundaries are designed to detect a hazard ratio (experimental vs. control) of 0.725 with approximately 85% power. Overall, 378 OS events (deaths) are required to be observed; this assumes a median (intent to treat [ITT]) OS of 30.3 months for the experimental arm (neratinib plus capecitabine) and 22.0 months for the control arm (lapatinib plus capecitabine).

Approximately 600 subjects will be enrolled and randomized equally between the two treatment arms. This sample size assumes a 1% drop out rate per 12 months (52 weeks) equally distributed between the treatment arms for the PFS endpoint.

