8.3. Analysis Methods

The significance levels allocated to the co-primary efficacy endpoints are 0.01 for PFS and 0.04 for OS. However, once the null hypothesis for PFS is rejected at $\alpha = 0.01$ at the time of the primary analysis then OS can be tested at the overall significance level of 0.05. The additional alpha propagated to the OS endpoint will not be spent at the interim OS analysis (Ye, 2013). The interim boundary for OS will remain the same as the boundary using the Lan-DeMets alpha spending function with overall $\alpha=0.04$ based on the actual information fraction (number of deaths as a proportion of the 378 target number of deaths). The time to CNS intervention will be tested after PFS and OS. If PFS is not significant and OS is, then time to CNS will be tested at $\alpha=0.04$; if both are significant, then time to CNS will be tested at $\alpha=0.05$. Unless OS is significant at the interim analysis, time to CNS intervention will not be tested at the primary PFS analysis (interim OS), and will only be tested after OS is significant at the final OS analysis (Figure 1).

Test of all other secondary endpoints are descriptive.

Figure 1: Testing Schema

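### After PFS success the protocol and the SAP set different final OS thresholds: 0.038 (overall 0.04) against about 0.049 (overall 0.05)

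*Protocol*

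**What the plan says.** Protocol 12.7 splits the error rate without any condition: "The co-primary endpoints will be analyzed using an overall Type I error rate of 0.01 for PFS and 0.04 for OS". Section 12.3.1.1 and the synopsis paragraph on the interim analysis then test OS "at the alpha level of 0.002 at the interim analysis and 0.038 for the final analysis". The synopsis efficacy paragraph repeats the final level, testing for "no difference in the hazard between the two treatment groups at the alpha level of 0.038". The 12.7 table pairs 0.002 with z 3.066 at 185 deaths, and 0.038 with z 2.058 at 378 deaths. The only adjustment the protocol provides is in 12.6, where Lan-DeMets spending changes the boundary "if the timing based on the final PFS analysis does not correspond to the expected information time of half of the OS events".

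SAP 8.3 adds a rule. Once PFS is rejected at 0.01, "then OS can be tested at the overall significance level of 0.05", and "The additional alpha propagated to the OS endpoint will not be spent at the interim OS analysis". The footnote to SAP Table 1 agrees: "This significance level relates to the 0.04 alpha allocation to OS but will be updated if the entire 0.05 can be allocated to OS". That table has the same two z values as the protocol but labels the final one 0.039. SAP 2.6 says that at 50% of deaths "the boundary using the Lan-DeMets alpha spending function is shown in Table 1 for OS interim analysis". SAP Section 11 is a placeholder with no entry.

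**The concern.** OS is co-primary, so its rejection threshold should be the same wherever it is written. Here it depends on which document is cited, and only in the case where PFS succeeds, which the design expects about 85% of the time under its own assumption. The choice would then be argued after the OS result is known.

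More than the OS claim depends on it. Under SAP 8.3, time to CNS intervention, the only secondary endpoint tested formally, is tested only if OS is significant.

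Two smaller matters sit in the same text. The protocol writes 0.038 as the test level, although its own 12.6 makes the boundary depend on when the interim falls. The printed z and p for the final look also do not correspond.

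**Working it through.** **Inputs.** 378 deaths in total and 185 expected at the interim, shown as 50% information (185/378 = 0.489; exactly half is 189). Two-sided overall alpha 0.04, or 0.05 after PFS success. OS hazard ratio 0.725; PFS hazard ratio 0.70 with 419 events at alpha 0.01; 1:1 randomisation. All are from Protocol 12.7, SAP 2.6 and SAP 8.3.

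**Plan's own figures.**
- Freedman's formula gives 419 PFS events exactly, and 376 deaths for OS at a fixed 0.04, close to the planned 378.
- z 3.066 is two-sided p 0.00217, which agrees with the printed 0.002.
- z 2.058 is two-sided p 0.0396. A level of 0.038 needs z 2.075, and 0.039 needs z 2.064.
- The 0.038 equals 0.04 − 0.002. That it arose by this subtraction is an inference.

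**Boundaries.** Lan-DeMets O'Brien-Fleming-type spending, 0.02 per side. Per-side spend at information t is 2[1 − Φ(z₀.₉₉/√t)]. The final z solves P(either look crosses) = 0.02 per side, with correlation √t between looks. Under the SAP rule the interim z is kept and the final z is solved again for 0.025 per side.

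| t | interim z | final z (p), overall 0.04 | final z (p), overall 0.05, interim kept |
|---|---|---|---|
| 0.40 | 3.498 | 2.055 (0.0398) | 1.961 (0.0499) |
| 0.489 | 3.127 | 2.060 (0.0394) | 1.964 (0.0495) |
| 0.50 | 3.090 | 2.061 (0.0393) | 1.965 (0.0494) |
| 0.60 | 2.786 | 2.072 (0.0383) | 1.972 (0.0486) |
| 0.70 | 2.547 | 2.089 (0.0367) | 1.983 (0.0473) |

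The Lan-DeMets pair at 50% is therefore 3.090/2.061, not the 3.066/2.058 in SAP Table 1. Classical O'Brien-Fleming at 50% gives 2.924/2.068 (p 0.0035/0.0386), which does not match either.

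**Critical hazard ratio**, exp(−2z/√378): 0.808 at level 0.038, 0.809 at 0.0393, 0.817 at 0.0494.

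**Chance of a disputed result.** This is the probability that the interim is not crossed and the final z falls between the two thresholds, at t = 0.50. The final z has mean −ln(HR)·√378/2, which is 3.126 at 0.725.

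| True OS HR | SAP rule against Lan-DeMets 0.0393 | SAP rule against printed 0.038 |
|---|---|---|
| 0.725 | 2.0% | 2.4% |
| 0.75 | 2.8% | 3.2% |
| 0.80 | 3.7% | 4.3% |

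The gap matters only after PFS success, so the first column was also computed conditional on it: 4 million simulated draws, PFS hazard ratio 0.70 (power 0.859), and PFS/OS log-rank correlation 0 to 0.6. The correlation is an assumption, since the documents give none. The results are 1.6–2.0%, 2.5–2.8% and 3.7–3.9%.

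**Overall OS error at t = 0.50.** Levels 0.002/0.038 spend 0.0387; 0.002/0.039 spend 0.0397; z 3.066/2.058 spend 0.0403.

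**If 0.038 were read as a constant** while the interim boundary is recomputed, overall error would pass 0.04 beyond about 62% information (235 deaths) and reach 0.0412 at 70%. A fixed 0.0393 would give 0.0410 at 60%.

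**The case against.** The strongest reply is that nothing is invalid. The recycling is prespecified in the SAP, cites a group sequential Holm procedure, releases the extra 0.01 only after PFS is rejected and does not spend it at the interim, so family-wise error stays within 0.05. The Table 1 footnote discloses it. Protocol Section 12 leaves further analysis detail to the SAP and promises that deviations will be identified in the study report. All of that stands, and it is why this is a conflict between documents and not an inflation of error. It does not settle which threshold applies. An overall alpha for a co-primary endpoint is more than detail, SAP Section 1 describes the SAP as supplementing the protocol, and no clause found gives the SAP precedence.

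The reply on timing is also partly right. Protocol 12.6 already provides for adjustment, and no section tells anyone to recompute the interim while freezing the final level. The inflation beyond 62% information is therefore hypothetical. At the planned timing 0.038 is conservative.

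On the tables, the SAP's 0.039 is correct to three decimals for Lan-DeMets at 50%, and the interim row agrees after rounding. Protocol 12.7 names O'Brien-Fleming boundaries and brings in Lan-DeMets only when timing departs from half, so printing Lan-DeMets values there is a choice of boundary family. It is a reasonable one, because the SAP uses Lan-DeMets and the planned 185 deaths are 48.9%, not half.

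**Conclusion.** The concern holds. After PFS success, with the interim near 50% information, a final OS p between 0.038 (0.039 on the Lan-DeMets calculation) and about 0.049 is a success under the SAP and a failure under the protocol. Such a result would occur in roughly 2% to 4% of trials at true OS hazard ratios of 0.725 to 0.80. If PFS is not rejected there is no material conflict. The z/p mismatch in the tables is nearly immaterial alone (critical hazard ratio 0.808 against 0.809).

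The figures rest on proportional hazards, the usual normal approximation to the log-rank statistic, per-side Lan-DeMets spending and an interim at 49–50% of deaths. Other spending conventions put the recycled final level at 0.048 to 0.049, which does not change the conclusion. This should be fixed before OS is analysed.

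**What to change.** 1. State one OS rule in both documents: overall 0.04 if PFS is not rejected and overall 0.05 if it is, with the interim boundary kept at the 0.04 plan. At the least, record this rule in SAP Section 11 as a change from the protocol.
2. In the protocol synopsis and Section 12.3.1.1, replace the fixed 0.038 with the Lan-DeMets final level computed from the actual number of deaths at each look. Do not substitute another constant.
3. In the Protocol 12.7 table and SAP Table 1, name the boundary family and print z and p that agree at the stated information. With Lan-DeMets these are 3.090/0.0020 and 2.061/0.0393 at 189 deaths, or 3.127/0.0018 and 2.060/0.0394 at 185. Add the recycled value (about z 1.965, p 0.0494 at 189 deaths), marked as planning only.

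The cost is wording and table entries. Sample size, event counts and analyses do not change. Power at hazard ratio 0.725 with 378 deaths is 85.7% at overall 0.04 and 87.8% with recycling. The protocol edits would need an amendment with ethics approval under Protocol 14.3.1; the Section 11 entry would not, and it is the quickest way to remove the ambiguity.

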12.3.2 Secondary Efficacy Analyses

The secondary efficacy endpoints include Investigator-assessed PFS, ORR, DOR, and CBR (CR, PR or SD \geq 24 weeks).

The secondary efficacy assessments include:

- The comparison of clinically relevant improvements in breast cancer patients with respect to radiographic changes or changes in other appropriate modalities, including ORR, DOR and CBR (CR or PR or SD \geq 24 weeks).
- In addition, time to onset of symptomatic metastatic CNS disease and the quality of life instruments EORTC QLQ-C30, BR23, and EuroQol EQ-5D-5L will be analyzed.

12.3.2.1 Statistical Methods

The treatment difference in the secondary efficacy endpoints of ORR and CBR will be analyzed using a Cochran-Mantel-Haenzel (CMH) Chi-square test, stratified by hormone receptor status, number of prior HER2-directed regimens in the metastatic setting, geographic region, and disease state (visceral vs. non-visceral only). The treatment difference in the secondary efficacy endpoints of DOR and PFS from Investigator-assessed PD will be analyzed using a product limit estimate of the median time to event. Differences between treatment groups will be examined using a log-rank test statistic stratified by hormone receptor status, number of prior HER2-directed regimens in the metastatic setting, visceral disease status, and geographic region strata (similar to the analysis for the primary endpoints). All time-to-event endpoints, including time to intervention for symptomatic CNS disease, will be displayed using a Kaplan-Meier survival plot. Health outcomes assessments (EORTC QLQ-C30, EORTC QLQ-BR23 and EQ-5D-5L) will be analyzed using a random effects mixed model with treatment, time, number of prior HER2-directed regimens in the metastatic setting (binary), geographic region, disease category, and the treatment by time interaction. Endpoints that could be affected by missing values (e.g., health outcomes assessments) will be analyzed using a sensitivity analysis to quantify the impact of missing values in the results.

12.4 Safety Analyses

Patients receiving at least 1 dose of investigational product will be evaluable for safety.

12.4.1 Investigational Product Exposure

Extent of exposure to each investigational product will be summarized by total dose, number of cycles, number of missed doses, number of dose delays, number of dose reductions.

12.4.2 Adverse Events

Safety will be assessed based on medical history, vital sign measurements, physical examination findings, ECG results, MUGA or ECHO, liver function test results, ECOG performance status, and laboratory assessments. Adverse events and SAEs will be reported until 28 days after the last dose of investigational product(s) and will be followed until resolution or until condition stabilizes. Should an Investigator be made aware of any SAE occurring any time after the reporting period, it must be promptly reported.

All safety endpoints will be summarized by treatment group and visit when appropriate. Adverse events and SAEs will be coded using the Medical Dictionary for Regulatory Activities (MedDRA) coding system v.15 or later and will be tabulated by system organ class (SOC) and preferred term. All AEs will be graded according to the NCI CTCAE v.4.0. Differences in the incidence of the most common AEs and SAEs between the two treatment groups will be investigated using a CMH chi-square test, stratified on hormone receptor status, prior number of HER2-directed regimens in the metastatic setting, geographic region, and visceral or non-visceral only disease.

A patient who experiences the same AE more than once within a SOC or preferred term category will be counted only once, using the worst toxicity grade for that event.

Serious adverse events and deaths will be provided in a listing. Treatment-emergent adverse events (TEAEs) leading to treatment discontinuation, dose modification, dose hold, and/or delay of investigational product will be tabulated by SOC, PT, and treatment group.

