- Objective response rate (ORR), duration of response (DOR) and clinical benefit (CBR) (complete response [CR] or partial response [PR] or stable disease [SD] ≥ 24 weeks).
- Time to intervention for symptomatic metastatic central nervous system (CNS) disease.
- Safety (adverse events [AEs], serious adverse events [SAEs]).
- Health outcomes assessments.

Exploratory:

The exploratory objective of this study is:

- To assess the population pharmacokinetics (PK) of neratinib when administered in combination with capecitabine.
-

Study Design:

This is a randomized, multi-center, multinational, open-label, active-controlled, parallel design study of the combination of neratinib plus capecitabine versus the combination of lapatinib plus capecitabine in HER2+ MBC patients who have received two or more prior HER2-directed regimens in the metastatic setting. Patients will be randomized in a 1:1 ratio to one of the following treatment arms:

- Arm A: neratinib (240 mg once daily) + capecitabine (1500 mg/m² daily, 750 mg/m² twice daily [BID])
- Arm B: lapatinib (1250 mg once daily) + capecitabine (2000 mg/m² daily, 1000 mg/m² BID)

Patients will receive either neratinib plus capecitabine combination or lapatinib plus capecitabine combination until the occurrence of death, disease progression, unacceptable toxicity, or other specified withdrawal criterion.

Patient randomization will be stratified according to:

- The number of previous HER2-directed regimens in the metastatic setting (N = 2 or N ≥ 3).
-

-
- Geographic region (North America vs. Europe, including Israel vs. Rest of World).
 - Visceral vs. non-visceral-only disease.
 - Estrogen receptor + (ER+) and/or progesterone receptor (PR+) (i.e., hormone receptor +) versus ER- and PR- (i.e., hormone receptor -).

Patients are anticipated to participate in the study for an average of 28 months. This includes approximately 0.5 months for screening, an estimated average of 9.5 months for the active treatment phase, and an estimated average of 18 months for the long-term follow-up phase. Treatment is to be given for as long as tolerated and while there is no disease progression. Patients who permanently discontinue treatment will enter the long-term follow-up phase until death or withdrawal of consent.

Investigational Product, Dose and Administration:**Neratinib + Capecitabine Combination:**

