9.3. Adverse Events, Serious Adverse Events, and Deaths

All AEs and SAEs will be reported until 28 days after the last dose of investigational product(s) and will be followed until resolution or until condition stabilizes. Should an Investigator be made aware of any SAE occurring any time after the reporting period, it must be promptly reported. The Patient Diary used for recording of investigational product intake will also be used by patients to document any AEs experienced during study treatment. In the case of diarrhea, it also serves to document the number of loose stools per day and use of loperamide/other antidiarrheal treatments taken.

AEs and SAEs will be coded using the most current version of MedDRA and tabulated by system organ class (SOC) and preferred term (PT). All AEs will be graded by the Investigator according to the NCI CTCAE v.4.0. Summaries will in general focus on treatment emergent adverse events (TEAEs). A TEAE is any adverse event that occurs or worsens on or after first dose of investigational product and up to 28 days after the last dose.

TEAEs and SAEs will be tabulated by SOC, PT, and treatment group. All tabulations will be sorted by descending frequency of SOC and PT in the total column unless otherwise noted. TEAEs will also be summarized according to relationship to study drug and severity. TEAEs of toxicity grade 3 or higher will also be summarized.

Similarly, treatment emergent adverse events leading to treatment discontinuation, dose modification, dose hold, and/or delay of investigational product will be tabulated by SOC, PT and treatment group.

Separate summaries and comparisons between treatment groups will be presented for treatment emergent diarrhea events leading to treatment discontinuation, dose holds, dose reductions, and delay of investigational product. Therapies used to treat diarrhea will also be summarized using descriptive statistics and compared between treatment groups.

SAEs, and TEAEs will be listed in by patient listings sorted by treatment, patient ID and study day; SAEs will be flagged. All AE listings will include study day, SOC, PT, reported term, dose, Cycle/day, AE onset date, AE resolution date, outcome, duration, relationship to drug, action taken, and severity.

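### The AE and SAE comparison takes no account of time at risk, although treatment runs to progression and the plan assumes median PFS of 8.0 v 5.6 months

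*Protocol*

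**What the plan says.** - **The test.** Protocol 12.4.2: "Differences in the incidence of the most common AEs and SAEs between the two treatment groups will be investigated using a CMH chi-square test". It is stratified on the four randomization factors and has no exposure term.
- **The outcome.** Same section: "A patient who experiences the same AE more than once within a SOC or preferred term category will be counted only once". Each patient is therefore a yes or a no.
- **The window.** Same section: "Adverse events and SAEs will be reported until 28 days after the last dose of investigational product(s"). SAP 9.3 defines treatment-emergent events over the same period.
- **Treatment duration.** Protocol synopsis, Study Design: "Treatment is to be given for as long as tolerated and while there is no disease progression".
- **The design assumption.** Protocol 12.7 gives, for neratinib, "this assumes a median (ITT) PFS of 8.0 months (34.7 weeks) for the experimental arm (neratinib plus capecitabine") and, for lapatinib, "5.6 months (24.3 weeks) for the control arm (lapatinib plus capecitabine").
- **The SAP.** Section 9.3 does not repeat the CMH test. However, SAP Section 1 describes the SAP as a supplement to the protocol, and Section 11 records no change, so the test stands. On diarrhea, SAP 9.3 adds: "Separate summaries and comparisons between treatment groups will be presented for treatment emergent diarrhea events", with no method named.
- **Exposure.** Protocol 12.2.3 and 12.4.1 and SAP 7 and 9.2 summarize it by arm. The table lists of the SAP and the supplemental SAP contain no exposure-adjusted AE rate and no cumulative incidence of AEs. The nearest item is a summary of time to first diarrhea, overall and by severity.

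**The concern.** Comparing safety between the arms is a secondary objective (Protocol 3.2). An ever/never comparison over unequal observation periods mixes two things: how toxic a month of treatment is, and how many months patients stay on it. If neratinib prolongs PFS as planned and patients stay on drug longer, it can show more patients with an event at the same monthly rate. If patients leave neratinib early, a higher monthly rate can disappear. The CMH strata are baseline factors and cannot correct a difference in follow-up that arises after randomization. A reader of the safety tables would see a p-value without knowing which of the two it reflects.

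**Working it through.** **1. The plan's own figure.** Protocol 12.7: "To detect a hazard ratio (control versus treatment) of 0.70 with approximately 85% power, 419 PFS events (PD/deaths) are required to be observed". Freedman's formula, two-sided 0.01 and 85% power: (2.576 + 1.036)² × (1.70/0.30)² = 419. This reproduces the plan. The medians behind it have ratio 8.0/5.6 = 1.43. The documents give no figure for the AE test.

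**2. Does treatment time follow PFS?** No duration by arm is stated. With exponential PFS at the planned medians, the mean over both arms is (8.0 + 5.6)/(2 ln 2) = 9.8 months. Protocol 4.1 expects an average of 9.5 months of active treatment. This supports the link but does not prove it.

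**3. Incidence at an equal monthly hazard.** Let λ be the AE hazard per month in both arms, μ = ln 2/median (0.0866 for neratinib, 0.1238 for lapatinib), and w = 28 days = 0.92 months.

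P(at least one event) = 1 − exp(−λw) × μ/(μ + λ)

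**4. Chance of a significant difference.** Assume n = 300 per arm (600 randomized 1:1, all treated) and two-sided 0.05; the documents give no level for safety tests.

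Chance = Φ{[(p_N − p_L) − 1.96·√(2p̄(1−p̄)/n)] / √[p_N(1−p_N)/n + p_L(1−p_L)/n]}

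Example, λ = 0.05:
- p_L = 1 − 0.955 × 0.1238/0.1738 = 0.320
- p_N = 1 − 0.955 × 0.0866/0.1366 = 0.394
- Chance = Φ[(0.0747 − 1.96 × 0.0391)/0.0390] = Φ(−0.05) = 0.48

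| λ per month | Lapatinib | Neratinib (8.0 v 5.6) | Significant, neratinib higher | Neratinib (6.8 v 5.6) | Significant, neratinib higher |
|---|---|---|---|---|---|
| 0.01 | 8.3% | 11.2% | 22% | 9.8% | 9% |
| 0.03 | 21.7% | 27.7% | 40% | 24.8% | 15% |
| 0.05 | 32.0% | 39.4% | 48% | 35.9% | 17% |
| 0.12 | 54.5% | 62.5% | 50% | 58.9% | 19% |

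The last two columns assume that treatment gains half of the PFS gain: 5.6 + 2.4/2 = 6.8 months.

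**5. Check by simulation.** A 24-stratum CMH test (2,000 replicates per setting, equal hazards, 8.0 v 5.6 months) found significantly more on neratinib in 24%, 37%, 46%, 52%, 42% and 19% of trials, at lapatinib incidences of 10%, 20%, 30%, 50%, 70% and 90%. On the same data, comparing first events per patient-month at risk rejected in 4.4% to 6.5%, about the nominal 5%.

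**6. Other sensitivities.**
- Data cut with 8 to 26 months of follow-up (assumed): 13% to 39%, for lapatinib incidences of 10% to 80%.
- AE hazard confined to the first 1–3 months: 2.5% to 5%, against 2.5% in that direction with no difference in incidence.

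**7. The opposite direction.** Suppose early stopping cut median neratinib treatment to 4.0 months (assumed, μ = 0.1733), with a hazard 1.4 times as high (0.07 v 0.05). Then p_N = 1 − exp(−0.07 × 0.92) × 0.1733/0.2433 = 33.2%, against 32.0% on lapatinib. A 40% higher rate shows as about one percentage point.

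**The case against.** **The test is not wrong for what it tests.** Its null is equal incidence. In the scenarios above the true incidences differ, so a rejection is a correct answer about incidence, which is a legitimate safety quantity. This stands. A reader might take 22–50% as the false-positive rate of the CMH test; it is not. It is how often a real difference in incidence, produced wholly by time at risk, would reach nominal significance.

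**The link from PFS to treatment time is inferred.** Under Protocol 10.1 treatment also stops for repeated dose reductions, long holds or request. This stands too, and it is why the half-gain case is shown. A reader might infer that neratinib will be made to look worse; the documents do not settle the direction.

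**The main toxicity starts early.** Protocol 7.1.1 says so for diarrhea, and Protocol 2.2.3.4 reports a median onset of 2 days in the Phase 1/2 study. For such events time at risk hardly matters. The point concerns events that accrue over treatment, and SAEs.

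**Unequal exposure will be visible.** Duration and cycles are tabulated by arm, and supplemental SAP 6.2 adds time to treatment discontinuation. This helps a careful reader, but nothing connects exposure to the AE comparison.

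**No controlled claim rests on an AE p-value.** SAP 8.3 controls error for PFS, OS and time to CNS intervention only. An inference that the trial's type I error is inflated would be unfounded.

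**Conclusion.** The point holds as a gap in the safety analysis. The planned test is valid for incidence over the treatment course, but it does not separate longer treatment from a higher toxicity rate, and no planned analysis does so. At equal, constant monthly hazards, the chance of a nominally significant excess on neratinib is about 22–50% if treatment time follows the planned PFS, about 9–19% if it lengthens half as much, and about 2.5–5% for early-onset events. Those figures rest on exponential treatment times, 300 patients per arm and two-sided 0.05. Shorter neratinib exposure would mask toxicity instead. The consequence is a safety comparison that is hard to interpret; the efficacy conclusions are not affected. It is a cheap improvement worth making.

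**What to change.** In Protocol 12.4.2 and SAP 9.3:

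1. Keep the crude incidence tables. Label any CMH p-value as descriptive and not adjusted for exposure.
2. For the most common AEs and SAEs, add first-event rates per 100 patient-months at risk by arm, with the rate difference or ratio and its 95% CI.
3. For all these AEs, add incidence in one early window stated in advance, for example Cycles 1–2. Rates alone would dilute early-onset events such as diarrhea in the longer-treated arm. Applying the window to every listed AE avoids having to classify events as early-onset.
4. If Aalen-Johansen curves are used, with end of AE follow-up as the competing event, read them at that early fixed time. Read late, they return the same gap. Ignoring the 28-day tail, λ/(λ + μ) × [1 − exp(−(λ + μ)t)] with λ = 0.12 and t = 24 months gives 57.7% v 49.1%, significant in about 56% of trials by the formula used above.

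**Cost.** A few extra tables from AE onset dates and dosing records already collected. The rates assume a roughly constant hazard, which the early window partly offsets.
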